## Statistical Analysis Plan

Analysis Designation	Endpoint	Model	Imputation Process Used	Off-trial Medication Data Included	Analysis Set
Secondary 1 - by Subgroups	FVC Absolute Change from Baseline	MMRM by Subgroups (see Section 6.6)	IUDR (trial withdrawal reason)/BOCF	Yes	ITT
Secondary 2 Hierarchical	Time to First PDPE	Cox's Proportional Hazards	censoring at date of last participation	Yes	ITT
Secondary 2 - Supportive	Time to First PE	Cox's Proportional Hazards	censoring at date of last participation	Yes	ITT
Secondary 2 - by Subgroups	Time to First PDPE	Cox's Proportional Hazards by Subgroups (see Section 6.6)	censoring at date of last participation	Yes	ITT
Secondary 3 Hierarchical	Number of Days of Antibiotic Use Due to PDPE	Negative Binomial Model	None	Yes	ITT
Secondary 3 - Supportive 1	Number of Days of Antibiotic Use Due to PDPE Excluding Overlaps	Negative Binomial Model	None	Yes	ITT
Secondary 3 - Supportive 2	Number of Days of Antibiotic Use Due to PE	Negative Binomial Model	None	Yes	ITT
Secondary 3 - Supportive 3	Number of Days of Antibiotic Use Due to PE Excluding Overlaps	Negative Binomial Model	None	Yes	ITT
Secondary 3 - by Subgroups	Number of Days of Antibiotic Use Due to PDPE	Negative Binomial Model by Subgroups (see Section 6.6)	None	Yes	ITT

## Statistical Analysis Plan

Analysis Designation	Endpoint	Model	Imputation Process Used	Off-trial Medication Data Included	Analysis Set
Secondary 4 Hierarchical	Number of Days in Hospital Due to PDPE	Negative Binomial Model	None	Yes	ITT
Secondary 4 - Supportive	Number of Days in Hospital Due to PE	Negative Binomial Model	None	Yes	ITT
Secondary 4 - by Subgroups	Number of Days in Hospital Due to PDPE	Negative Binomial Model by Subgroups (see Section 6.6)	None	Yes	ITT
Secondary 5 Hierarchical	PDPE Rate	Negative Binomial Model	Half historical count over 26 weeks for withdrawals before Week 14 or one quarter historical count over 26 weeks for withdrawals after Week 14	Yes	ITT
Secondary 5 - Sensitivity 1	PDPE Rate	Negative Binomial Model	None	Yes	ITT

### Statistical Analysis Plan

Analysis Designation	Endpoint	Model	Imputation Process Used	Off-trial Medication Data Included	Analysis Set
Secondary 5 - Sensitivity 2	PDPE Rate	Zero Inflated Negative Binomial Model	Half historical count over 26 weeks for withdrawals before Week 14 or one quarter historical count over 26 weeks for withdrawals after Week 14	Yes	ITT
Secondary 5 - Sensitivity 3	PDPE Rate	Negative Binomial Model	Multiple imputation based on historical PE count	Yes	ITT
Secondary 5 - Supportive	PE Rate	Negative Binomial Model	Half historical count over 26 weeks for withdrawals before Week 14 or one quarter historical count over 26 weeks for withdrawals after Week 14	Yes	ITT

## Statistical Analysis Plan

Analysis Designation	Endpoint	Model	Imputation Process Used	Off-trial Medication Data Included	Analysis Set
Secondary 5 - by Subgroups	PDPE Rate	Negative Binomial Model by Subgroups (see Section 6.6)	Half historical count over 26 weeks for withdrawals before Week 14 or one quarter historical count over 26 weeks for withdrawals after Week 14	Yes	ITT
Secondary Non-hierarchical					
Secondary Non-hierarchical 1	Incidence of PDPEs	Logistic Regression	None	Yes	ITT
Secondary Non-hierarchical 1 - Supportive	Incidence of PEs	Logistic Regression	None	Yes	ITT
Secondary Non-hierarchical 2	Ease of Expectoration VAS Score Absolute Change from Baseline	MMRM	IUDR (trial withdrawal reason)/BOCF	Yes	ITT

Statistical Analysis Plan

Analysis Designation	Endpoint	Model	Imputation Process Used	Off-trial Medication Data Included	Analysis Set
Secondary Non-hierarchical 2 - Sensitivity	Ease of Expectoration VAS Score Absolute Change from Baseline	MMRM	None	Yes	ITT
Secondary Non-hierarchical 3	CFQ-R Respiratory Domain Scaled Score Absolute Change from Baseline	MMRM	IUDR (trial withdrawal reason)/BOCF	Yes	ITT
Secondary Non-hierarchical 3 - Sensitivity	CFQ-R Respiratory Domain Scaled Score Absolute Change from Baseline	MMRM	None	Yes	ITT
Secondary Non-hierarchical 3 - Supportive	CFQ-R Respiratory Domain Scaled Score Excluding Question 42 Absolute Change from Baseline	MMRM	IUDR (trial withdrawal reason)/BOCF	Yes	ITT

## Statistical Analysis Plan

### 9. SAFETY

The SAF set will be used for all safety analyses. Safety will be assessed on the basis of AE reports, extent of exposure and compliance, physical examinations, and vital signs.

No inferential statistical testing is planned on the safety data.

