8.1.2.1 Baseline (Visit 1)

Visit 1 will occur 2 to 5 weeks post screening visit

Prior to the visit, confirm medication-withholding periods have been adhered to (including 2-weeks wash out from hypertonic saline). If not, the subject's visit should be postponed.

*Confirm that the subject is **not** currently having a pulmonary exacerbation. In the event of a pulmonary exacerbation, visit 1 should occur 2 to 5 weeks from the end of the treatment for the exacerbation or of the adverse event, whichever is later.*

The following procedures will be performed:

- Review subject diary.
- Randomize eligible subjects if compliance with maintenance therapies (antibiotic & rhDNase) is at least 80% in the two weeks prior to visit 1 using the *Subject Diary*;
- Review concomitant medications, and adverse events; (including pulmonary exacerbations or hemoptysis);
- Complete ease of expectoration VAS and respiratory domain of the CFQ-R questionnaire;
- Conduct physical examination (chest sounds, weight, BP, HR, O₂ saturation, temperature, respiratory rate);
- Perform pre-mannitol pulmonary function testing (FEV₁, FVC, PEF, FEF₂₅₋₇₅);
- Assign IMP using IWRS;
- Dispense IMP and bronchodilator according to randomization schedule;
- Premedicate with four puffs of albuterol/salbutamol from a metered dose inhaler (MDI) (360-400µg), 5 to 15 minutes prior to each dose of IMP. The subject's preferred bronchodilator may be used as an alternative premedication. Care must be taken to ensure that a bronchodilator is used prior to ALL doses of IMP;

- Train the subjects on correct administration and inhalation of IMP, then administer initial dose of IMP (mannitol/control) according to ‘IMP Administration Procedure’ (see Section 6.1 figure 2) and randomization number; IMP administration should not be performed by the same person who administers the MTT.
- Perform pulmonary function test 30 minutes post dose. If the subject has a measured fall in FEV1 >20% at 30 minutes post dose completion, no further study medication should be administered. The subject should be continued in the study on an intention to treat basis. Symptomatic bronchoconstriction should be managed as medically appropriate. The respiratory technician performing spirometry could be the same person who administers the IMP as long as they have not performed the MTT.
- Access IWRS to complete the required visit information.

8.1.2.2 📞 Phone call 2 weeks after visit 1 (Week 2 ± 3 days)

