- Perform pulmonary function test 30 minutes post dose. Symptomatic bronchoconstriction should be managed as medically appropriate;
- Conduct drug accountability; *and*
- Access IWRS to complete the required visit information.

8.1.2.12 📞 Final phone call 1 week after visit 4 (Week 27 ± 1 day)

One week after the final visit of the trial, the Investigator or designate, will call the subject to:

- Collect information on any adverse events experienced (including pulmonary exacerbations or hemoptysis); and
- Collect information on current concomitant medications; *and*
- Discharge subject from trial.

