8.3.1 Safety evaluations

Any clinically significant change in safety evaluation will be recorded as an adverse event (AE) as detailed in Section 8.3.1.1.

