8.3.2 Criteria

An assessment of safety will be made on the basis of reviewing changes in physical examination, spirometry and using adverse event data.

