### 4.3. SAFETY ENDPOINTS

Safety endpoints include adverse events (AEs; including deaths), extent of trial medication exposure and trial medication compliance, vital signs, and physical examination data.

\*Updated in this SAP to be reported in L rather than mL to match the units used in data collection (see Section 11).

\*\*Clarified in this SAP that pulmonary exacerbations classified as protocol defined pulmonary exacerbations (PDPEs) will be used in the main analyses for these endpoints (see Section 11).

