### 6.2.4. Baseline

The baseline value for all efficacy endpoints will be taken as Visit 1. It will be assumed that assessments performed on this visit were prior to first trial medication administration, with the exception of post-dose spirometry. Therefore, efficacy baseline will be the Visit 1 measurement unless the Visit 1 measurement is missing, where the Visit 0 measurement will be used as baseline.

The baseline value for safety endpoints (vital signs and physical examination) will be taken as the latest available measurement prior to or on Treatment Day 1 (i.e. day of first trial medication dose). It will be assumed that safety assessments performed on Treatment Day 1 were prior to trial medication administration. Baseline will be the Visit 1 measurement.

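### The protocol bases safety partly on spirometry and tests lung function 30 minutes after dosing at four visits, but the readable SAP has no by-arm summary of the post-dose FEV1 change or of falls above 20%

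*SAP*

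**What the plan says.** Protocol 8.3.2 states: "An assessment of safety will be made on the basis of reviewing changes in physical examination, spirometry and using adverse event data".

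The Visit 1 procedures (Protocol 8.1.2.1) include: "Perform pulmonary function test 30 minutes post dose. If the subject has a measured fall in FEV1 >20% at 30 minutes post dose completion". The stated consequence is that no more study drug is given and the subject stays in the trial. Visits 2 and 3 (8.1.2.4 and 8.1.2.7) carry the same test and rule. Visit 4 (8.1.2.11) keeps the test without the rule: "Perform pulmonary function test 30 minutes post dose. Symptomatic bronchoconstriction should be managed as medically appropriate".

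SAP 4.3 lists the safety endpoints: "Safety endpoints include adverse events (AEs; including deaths), extent of trial medication exposure and trial medication compliance, vital signs, and physical examination data". SAP 9 repeats that scope: "Safety will be assessed on the basis of AE reports, extent of exposure and compliance, physical examinations, and vital signs". Sections 9.1 to 9.5 then cover exposure, compliance, adverse events, vital signs and physical examination. The readable SAP mentions the post-dose measurement once, in 6.2.4, where Visit 1 assessments are assumed to precede the first dose "with the exception of post-dose spirometry". Section 11 lists 15 changes from the protocol, one as small as reporting in L instead of mL. Spirometry as a safety measure is not among them.

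**The concern.** Bronchoconstriction is the risk around which much of the protocol's conduct is built: a tolerance test at screening, a bronchodilator before every dose, and a measured threshold that ends treatment. Passing the screening test does not settle the matter. Under Protocol 8.1.1.1 a subject whose FEV1 falls by at least 20% but less than 50% after the full 400 mg still passes if it recovers within 15 minutes, so such subjects can be randomised. The 30-minute tests are the only scheduled, measured evidence, by arm, of how FEV1 responds acutely to the randomised doses.

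If the SAP is followed as written, the report need not say how many subjects on 400 mg or 50 mg had a measured fall above 20%, how large the changes were, or how many falls led to stopping drug. Protocol 1.2 gives prospective evidence of safety as an aim of the trial.

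**Working it through.** **1. Protocol and SAP side by side**

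| Item | Protocol | Readable SAP |
|---|---|---|
| Spirometry as a basis for safety | Yes (8.3.2) | Absent from 4.3 and 9 |
| Visits with a 30-minute post-dose test | 4 (Visits 1 to 4) | Post-dose values mentioned once, to set them apart from baseline (6.2.4) |
| Visits where a fall above 20% ends drug | 3 (Visits 1 to 3) | No count of such falls |
| Omission declared as a change | – | Not in Section 11 |

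**2. Could another planned output show the same thing?**

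- *Adverse events.* Protocol 8.3.1 requires clinically significant changes in safety evaluations to be recorded as adverse events. SAP 9.3 tabulates these by system organ class and preferred term, and SAP 6.1 presents safety data by arm. The visit text, however, does not say that a fall above 20% must be recorded as an adverse event, whereas the tolerance test text (8.1.1.1) does say which findings must be.
- *Discontinuations.* SAP 7.1.3 tabulates reasons for stopping drug. They are the CRF reasons, which the documents do not list, so an FEV1 fall may not be identifiable.
- *Efficacy summaries.* SAP 8.1.1 and 8.2.1 summarise change from baseline for the efficacy endpoints at Weeks 6, 14 and 26, not the change across a dose.
- *Tolerance test.* SAP 7.6 summarises maximum FEV1 fall by test result, before any arms exist.

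None of these gives the size of the post-dose change or the proportion with a fall above 20%.

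**3. What the missing table could show**

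The plan gives no figure for post-dose falls, so there is none to reproduce. Inputs: 423 randomised (SAP 10), 1:1 allocation, assumed to split 211 control and 212 mannitol because the split is not stated. The fall rates are assumptions.

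Upper bound on pre/post pairs: 4 × 423 = 1,692. The real number is lower because of withdrawals and discontinuations.

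Half-width = 1.96 × √[pC(1 − pC)/211 + pM(1 − pM)/212], where pC and pM are the control and mannitol proportions.

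| Control vs mannitol (assumed) | Standard error | Half-width | Difference and 95% interval (points) |
|---|---|---|---|
| 1% vs 2% | √(0.0099/211 + 0.0196/212) = 0.0118 | 2.3 points | 1 (−1.3 to 3.3) |
| 1% vs 5% | √(0.0099/211 + 0.0475/212) = 0.0165 | 3.2 points | 4 (0.8 to 7.2) |
| 2% vs 10% | √(0.0196/211 + 0.09/212) = 0.0227 | 4.5 points | 8 (3.5 to 12.5) |

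If no fall occurred among 211 subjects, the one-sided upper 95% limit would be 1 − 0.05^(1/211) = 1.4%.

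A small difference would be inconclusive; a larger one, or a reassuring absence of events, would be informative. At 1%, only 211 × 0.01 = 2.1 control events are expected, so the normal approximation is rough.

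**The case against.** A reader might infer that acute bronchoconstriction is never compared between arms. The documents do not support that: events recorded as adverse events, including related ones and those leading to discontinuation, are tabulated by arm, and reasons for stopping drug are reported. Nor do the post-dose data go unused. They drive individual treatment decisions at Visits 1 to 3, and SAP 2.2 says the DMC saw unblinded FEV1 and FVC summaries among the safety data, though not whether these included post-dose values.

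It can also be said that the SAP departs from little. Protocol 8.3.2 is one sentence and names no endpoint, threshold or table. Protocol 8.3.1 has no spirometry subsection, the method is described under Efficacy (8.2.1.1), and Protocol Section 10 plans no safety analysis of spirometry, while SAP Section 11 concerns changes to planned analyses. This has force. The point is a mismatch between Protocol 8.3.2 and SAP 4.3 and 9, not the removal of a specified analysis. It still leaves a safety measure named by the protocol, with a threshold that ends treatment, without a summary by arm.

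Two limits on the measure also stand. Pre-dose spirometry is done before the bronchodilator (8.2.1.1), so the change across a dose includes bronchodilation in both arms. And subjects who stop drug, including those stopped by the 20% rule, drop out of later dosing tests.

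Finally, the SAP appendices are redacted, so a table there cannot be excluded. The sections that define the safety endpoints are readable, however, and do not include spirometry.

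**Conclusion.** The concern holds as a gap in the safety analysis. The readable SAP omits spirometry from safety and specifies no by-arm summary of the 30-minute FEV1 change or of falls above 20%, although Protocol 8.3.2 relies on spirometry. Bronchoconstriction remains visible by arm through adverse event and discontinuation tables; what is lost is the measured change and any fall not recorded as an adverse event.

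How many falls that is cannot be known from the documents. The half-widths of 2.3 to 4.5 points rest on assumed rates and a near-equal split of 423, and 1,692 pairs is only a ceiling. The primary conclusion, error rate and sample size are not affected, but the change should be made: the omission is easily closed and concerns the risk the protocol guards against most closely.

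**What to change.** Add post-dose spirometry to SAP 4.3 and 9 and record the addition in Section 11. If the SAP can no longer be amended, report the tables as a labelled addition. On the Safety set:

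- Define percent change in FEV1 from the pre-dose value to 30 minutes after the dose at the same visit. State this reference value, since the visit text does not name it. Summarise by visit and arm.
- Give the number and percentage of subjects with a fall above 20% at Visit 1 and at any visit, with the between-arm difference and 95% confidence interval for estimation only. This adds no test, so it agrees with SAP 9. An interval suited to small counts is preferable.
- Of those subjects, report how many stopped trial medication and how many had a related adverse event.
- Treat the Visit 1 and any-visit counts as the randomised comparison, because Visits 2 to 4 taken singly include only subjects still on drug. Add a footnote that the pre-dose value precedes the bronchodilator in both arms.

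The cost is one or two descriptive tables from measurements the protocol already requires, with no new procedure and no effect on alpha or sample size.

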#### 9.1. EXTENT OF EXPOSURE

Duration of exposure (months) will be summarized and will be calculated for the SAF set as follows:

$$\text{Duration of exposure} = (\text{last date trial medication} - \text{first date trial medication} + 1) \times 12 / 365.25$$

Duration of exposure in months will be rounded to one decimal place for displaying purposes.

Duration of exposure will be summarized for the SAF set using summary statistics for continuous variables and also for categorical variables using monthly categories (e.g. 0-1, >1-2, etc.).

If last date of trial medication is missing or partial then the algorithm specified in Section 6.2.1 will be applied.

#### 9.2. TRIAL MEDICATION COMPLIANCE

Trial medication compliance (%) will be summarized for the SAF set using summary statistics for continuous variables. Compliance to trial medication while taking trial medication will be calculated based on the subject reported last date of trial medication as follows:

$$\text{Compliance} = 100\% \times \frac{\sum_{i=1}^3 (D_i) - \sum_{i=2}^4 (R_i)}{2 \times 10 \times ([\text{last date of trial med}^*] - [\text{date of Trial Day 1}] + 1)}$$

\* Date of last dose of trial medication is as defined in Section 6.2.1

where:

$D_i$  = number of capsules dispensed at Visit  $i$ .

$R_i$  = number of unused capsules returned at Visit  $i$ .

Pharmaxis Ltd

DPM-CF-303

Final v1.0

## Statistical Analysis Plan

This calculation assumes 10 capsules were to be taken at each trial medication administration time; dosing was b.i.d., hence 20 capsules were to be taken each day. Trial medication to be taken on dates corresponding with clinic visits are administered at the clinic. Unreturned capsules and/or blister packs will be assumed to have been used by the subject.

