6.1.4 Investigational medicinal product supply and accountability

Pharmaxis will provide the participating sites with sufficient amount of IMP.

The site Investigator must ensure that deliveries of investigational product from the Sponsor are correctly received by a responsible person (e.g., Pharmacist), that all receipts are recorded in writing, that the product is stored in a secure area under recommended and proper storage conditions, and that they are used in accordance with the protocol. It is the responsibility of the Investigator to ensure that the integrity of the investigational medication is not jeopardized prior to dispensing. The investigational medication must be dispensed as provided by the Sponsor with no further repackaging done at site.

The site Pharmacist / Investigator(s) / legally qualified designee, as documented on the Site Signature / Delegation of Authority Log, will dispense/administer the investigational medication only to subjects enrolled in this trial following the procedures set out in Section 6. The site Pharmacist / Investigator(s) is responsible for assuring the retrieval of all trial supplies from the subjects. Unused investigational medication(s) (opened, unopened, or empty capsules) must be returned to the Sponsor or destroyed on site (if appropriate) after the investigational medication accountability has been completed and destruction has been authorized by the Sponsor.

Trial drug accountability should be performed by counting the used (empty blisters) and unused trial drug remaining in blisters.

The Investigator(s) must maintain accurate and adequate records including dates of receipt and return of IMP shipments, and batch numbers and quantities received/returned from/to Pharmaxis, as well as dates and amounts dispensed to/returned by trial subjects. Destruction of trial supplies should not be done without prior approval from the Sponsor. Full accountability documentation (with witnessing) is required for all destroyed IMP at an investigator site.

The Investigator / site Pharmacist will be required to provide the Monitor with access to the investigational medication and records for periodic review.

Copies of the accountability records will be provided to the pharmacy monitor for inclusion in the trial master file.

It is forbidden to use investigational medication for purposes other than defined in this protocol.

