## Statistical Analysis Plan

### 3.7. ADMINISTRATION OF TRIAL MEDICATION

The inhalation technique for inhaled mannitol (400 mg b.i.d.) and control (50 mg inhaled mannitol b.i.d.) is identical.

The trial medication is to be administered in a standardized manner. The Investigator is responsible for instructing the subject on the correct trial medication inhalation technique, and on use of the bronchodilator (albuterol/salbutamol metered dose inhaler (MDI) or similar) 5 to 15 minutes prior to the trial medication administration.

The Investigator will prescribe the subject with a bronchodilator (albuterol/salbutamol-MDI or similar) to be used as premedication prior to inhalation of the trial medication. This bronchodilator may also be used in the event of post-treatment chest tightness.

Subjects will take trial medication twice a day, once in the morning and once in the evening. The evening dose should be administered approximately 2 hours before sleep.

[figure not shown]
Each kit dispensed contains additional supply to account for the protocol allowed visit windows.

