## Statistical Analysis Plan

All major protocol deviations, from [REDACTED] and programmed, will be listed and summarized for the ITT set based on the [REDACTED] category and assigned subcategory. Important minor protocol deviations, including those related to trial inclusion or exclusion criteria, conduct of the trial, subject management or subject assessments, were identified at the BDRM and will be listed by [REDACTED] category and assigned subcategory.

Criteria to determine if a subject will be included in the PP set were detailed in a BDRM preparation plan together with details of the programmatic listings to be prepared. The adjusted criteria confirmed during the BDRM to determine if a subject will be excluded from the PP set were:

- Did not meet all the inclusion and exclusion criteria.
- Was randomized but did not take at least one dose of trial medication.
- Compliance to trial medication while taking trial medication <60%.
- No valid baseline FEV1 measure, where a baseline measure was considered non valid if precluded medications were not withheld as detailed in the protocol.
- Started treatment with maintenance hypertonic saline where it was considered that there was a potential for efficacy assessments to be impacted.
- Started or stopped treatment with rhDNase or maintenance antibiotics where it was considered that there was a potential for efficacy assessments to be impacted.

Further details of the rules applied to determine inclusion in the PP set will be documented in the BDRM Highlights and will be agreed and finalized prior to database lock.

Only FEV1 measurements taken in the absence of precluded medications will be considered valid. Precluded medications and required withholding periods are detailed in Table 3 (as detailed in the protocol and CRF).

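### A subject dispensed at every scheduled visit who returns no drug scores about 100% compliance or more whatever was taken, so the 60% per-protocol cut cannot detect low intake in that subject

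*SAP*

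**What the plan says.** SAP 9.2 defines compliance as a ratio. The numerator is the sum over Visits 1 to 3 of the "number of capsules dispensed at Visit" i, minus the sum over Visits 2 to 4 of the "number of unused capsules returned at Visit" i. The denominator is 20 capsules times the days from Trial Day 1 to the last dose; the SAP explains that "dosing was b.i.d., hence 20 capsules were to be taken each day". The figure "will be calculated based on the subject reported last date of trial medication". For drug that does not come back the rule is: "Unreturned capsules and/or blister packs will be assumed to have been used by the subject". The formula has no cap at 100% and makes no exception for a lost or unreturned kit.

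SAP 5.5 lists among the reasons for exclusion from the PP set "Compliance to trial medication while taking trial medication <60" percent, the same term that 9.2 defines. SAP 3.7 states: "Each kit dispensed contains additional supply to account for the protocol allowed visit windows". Neither document gives the kit size.

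The protocol requires two further records that the formula does not use. Section 6.1.4 says: "Trial drug accountability should be performed by counting the used (empty blisters) and unused trial drug remaining in blisters". Section 6.1 asks subjects to enter the dates of missed doses in the diary.

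**The concern.** For anything not brought back, the score says nothing about intake. It reflects only what was handed out. Protocol 10.2.6 plans the PP analysis to estimate the effect of taking mannitol, as opposed to being randomized to it. Apart from having taken at least one dose, the 60% rule is the only criterion listed in SAP 5.5 that looks at intake. If it cannot see low intake in subjects who return nothing, the PP set may retain some of the subjects it was meant to exclude.

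Non-return is foreseeable. The protocol's Time and Events Schedule has no drug accountability at the IMP discontinuation visit and defers collection to the next scheduled visit. A subject who stops and does not attend that visit leaves nothing to subtract.

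The compliance table is exposed as well. The denominator stops at the last dose, but the numerator still counts the whole unreturned kit.

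**Working it through.** **Inputs.** Capsules per day: 2 doses × 10 = 20, which reproduces the SAP's figure. Visits 2, 3 and 4 fall on target days 43, 99 and 183 (SAP 6.4). The protocol's Visit 4 window of −7 to +28 days allows days 176 to 211. Supply per kit is an assumption, taken at three levels:

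- no surplus: 42, 56 and 84 days;
- surplus for a late visit (+7, +7, +28): 49, 63 and 112 days;
- surplus for the longest permitted interval (+7, +14, +35): 49, 70 and 119 days.

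**Formula.** Compliance = 100 × (dispensed − returned) / (20 × days to last dose). The denominator is 3,520 at day 176, 3,660 at day 183 and 4,220 at day 211.

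**All three kits dispensed, nothing returned:**

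| Supply (days) | Capsules dispensed | Day 176 | Day 183 | Day 211 |
|---|---|---|---|---|
| 42 + 56 + 84 = 182 | 3,640 | 103.4% | 99.5% | 86.3% |
| 49 + 63 + 112 = 224 | 4,480 | 127.3% | 122.4% | 106.2% |
| 49 + 70 + 119 = 238 | 4,760 | 135.2% | 130.1% | 112.8% |

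True intake does not enter any of these values. To score below 60%, the last dose would have to fall after day 182/0.6 = 303 with no surplus, or day 238/0.6 = 397 with the largest. Both lie beyond day 211.

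**Partial return, true intake 30%, last dose day 183.** Capsules taken: 0.3 × 3,660 = 1,098. If all unused capsules come back, the score is 30.0%. The 60% cut corresponds to 0.6 × 3,660 = 2,196 capsules counted as used.

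- No surplus: 3,640 − 1,098 = 2,542 are unused, and more than 3,640 − 2,196 = 1,444 must be returned, which is 56.8% of them.
- Largest surplus: 4,760 − 1,098 = 3,662 are unused, and more than 4,760 − 2,196 = 2,564 must be returned, which is 70.0%.

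**Only the last kit unreturned, true intake 40%, last dose day 183.** The first two intervals cover 98 days, so 0.4 × 20 × 98 = 784 capsules are taken and the rest returned. The score is (784 + 1,680)/3,660 = 67.3% with no surplus and (784 + 2,240)/3,660 = 82.6% with 112 days in the last kit. Both pass the cut.

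**Early stoppers with an unreturned first kit.** Last dose on day 7: 840/140 = 600% to 980/140 = 700%. Last dose on day 14: 840/280 = 300% to 980/280 = 350%. With 423 randomized (SAP 10), about 211 per arm, one subject scored at 600% instead of 100% raises an arm mean by 500/211 = 2.4 points.

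**Where a non-returner does fall below 60%.** With only the Visit 1 and 2 kits dispensed and a last dose on day 183, the score is 1,960/3,660 = 53.6% with no surplus and 61.2% to 65.0% with surplus. On day 211 it is 46.4% to 56.4%. With only the Visit 1 kit, the score drops below 60% once the reported last dose is after day 42/0.6 = 70 to 49/0.6 = 82, and is 23.0% to 26.8% at day 183.

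**The case against.** The strongest reply is that the SAP follows the protocol. Protocol 6.1.1 bases adherence on a returned medication count, and SAP 9.2 applies this and states its convention openly. That is true, but it does not make the result informative when nothing is returned.

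Counting empty blisters is no cure on its own. A subject who returns nothing has brought back no empties either, and an adherent subject who throws empties away would be scored too low. This stands, and it limits blister counts to a cross-check.

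PP status is not settled by the formula alone. SAP 5.5 has monitor-recorded and programmed deviations reviewed at a blind data review meeting (BDRM), and leaves further rules to a document not available here. A non-returner might be excluded on other grounds. This stands too, but the compliance figure put before that meeting would show the subject as compliant.

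The documents also provide for retrieval: sites are responsible for it and subjects are repeatedly reminded. How often kits go unreturned is unknown.

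A reader might infer that any non-returner always scores about 100% and can never be excluded by the 60% rule. The missed-dispensing cases above contradict this: the score can fall below 60%, and since the supply itself then limits true intake to less than 60%, the exclusion is correct. A reader might also infer that compliance is inflated more on mannitol. SAP 8.1.1 cites higher drop-out on the experimental treatment in the two previous studies, but nothing in either document links unreturned kits to arm, and inflation requires non-return as well as early stopping.

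**Conclusion.** The concern holds for a subject dispensed at every scheduled visit who returns nothing. At the planned day 183 the score is 99.5% with no surplus and about 122% to 130% with surplus covering the windows. The lowest value found across the Visit 4 window is 86.3%, at day 211 with no surplus at all, although the SAP says that surplus exists. The 60% rule therefore cannot detect low intake in these subjects. The kit sizes are assumptions, but the conclusion is the same at all three levels.

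The values of several hundred percent for early stoppers are a defect of the compliance summary, chiefly of its mean. They do not show wrong PP status, because the criterion concerns compliance while taking drug: someone who took every dose until day 7 passes it properly.

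The consequence is limited to the compliance summary and the supportive PP analysis, which SAP 8.1.3.1 describes as a robustness check. The ITT primary analysis is unaffected. Retaining poorly adherent subjects would ordinarily dilute a PP effect rather than favor mannitol. The point should be corrected, but it does not threaten the trial's main conclusion.

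**What to change.** Replace the assumption in SAP 9.2 that unreturned drug was used:

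- For an interval with an unreturned or unaccounted kit, derive intake from the missed-dose dates in the diary.
- If these are not available, set compliance for that interval to missing, flag the subject, and decide PP status blind at the BDRM. SAP 5.5 leaves the PP rules to be finalized before database lock, so the decision can be recorded there.
- Use returned empty blisters only as a cross-check, where they were brought back.
- Keep the present formula as a labelled upper bound.

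The cost is SAP wording and one derivation. The protocol requires the diary record, but neither document says that missed-dose dates are entered in the CRF, so data entry may be needed, and a subject who returns no drug may return no diary. Compliance will be lower or missing for some subjects, and the PP set may shrink slightly.
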